1.7 Rationale to Investigate PD 0332991 in Combination with Anastrozole

In preclinical studies, endocrine resistance was associated with persistent cyclin D expression and RB phosphorylation despite efficient blockade of ER and the poor prognosis luminal B breast cancers were associated with a gene expression signature of RB-dysfunction [20]. PD 0332991 was shown to have anti-tumor activity for multiple tumor types including breast cancer in both in vitro and in vivo studies [88, 89]. In preclinical studies, PD 0332991 was particularly effective in inhibiting cell growth of luminal breast cancer subtype [88]. A synergistic anti-tumor effect was also observed when combined with tamoxifen in tamoxifen-sensitive and resistant cell lines [88]. Importantly, treatment with PD 0332991 effectively suppressed proliferation of ER+ breast cancer cell lines resistant to anti-estrogen and led to irreversible cell cycle arrest and features of cellular senescence [20]. These studies provided a preclinical rationale to combine endocrine therapy and a Cdk4/6 inhibitor to improve tumor control for ER+ breast cancer.

[figure not shown]
The combination of PD 0332991 and endocrine therapy has shown highly promising results in patients with advanced ER+ HER2- breast cancer. In the randomized phase 2 study of letrozole with or without PD 0332991 as first line therapy for metastatic ER+, HER2- breast cancer, the PFS was significantly better in the combination arm (26.1 months vs 7.5

months (HR 0.37, 95% CI 0.21 – 0.63, $p<0.001$) [22]. The response rate for the combination arm ($n = 84$) was 31% vs. 26% for the letrozole arm ($n = 81$) and the clinical benefit rate was 68% vs. 44%, respectively. Toxicities were tolerable. The most commonly reported treatment-related AEs in the combination arm were neutropenia (grade 1/2: 23%; grade 3: 55%, grade 4: 6%), leukopenia (grade 1/2: 29%; grade 3: 17%, grade 4: 0%), anemia (grade 1/2: 24%; grade 3: 5%, grade 4: 1%), and fatigue (grade 1/2: 35%; grade 3: 2%, grade 4: 2%) and nausea (grade 1/2: 23%; grade 3: 2%, grade 4: 0%). The promising clinical data led to the FDA fast-track listing of PD 0332991.

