to recover to \leq grade 1 as well as to accommodate surgery scheduling. Anastrozole is continued in all patients during the neoadjuvant period. Patients who receive goserelin should also continue goserelin every 28 days during the neoadjuvant period.

CBC+D is to be performed 3 days (± 1 day) prior to surgery in patients who receive Cycle 5 therapy. Treatment with PD 0332991 should be interrupted if ANC $<$ 1,000/mcL, platelets $<$ 100,000/mcL, or patients present with any \geq grade 2 treatment-related toxicities. If a patient needs to stop treatment prematurely in Cycle 5, she will have surgery on the scheduled date unless contraindicated, as the recovery of neutropenia is usually prompt after stopping PD 0332991 due to its mechanisms of action (investigator brochure). However, surgery may be rescheduled at the discretion of the treating physician and the study chair. Patients should continue with anastrozole until the day before surgery regardless of whether they complete Cycle 5 of PD 0332991.

Patients whose ANC and/or platelets do not recover within 3 weeks following the completion of Cycle 4 will proceed to surgery as planned (3 to 5 weeks following the last dose of PD 0332991 (Cycle 4 Day 21)). For these patients, anastrozole is to be continued until the day of surgery, with the last dose of anastrozole given the day before surgery.

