6.3 Re-Treatment Criteria for Neoadjuvant Cycles 1-4 and Adjuvant Therapy

A new cycle of treatment with PD 0332991 may begin only if:

- ANC \geq 1,000/mcL.
- Platelet count \geq 50,000/mcL.
- Non-hematologic toxicities have returned to baseline or Grade \leq 1 severity (or, at the Investigator's discretion, Grade \leq 2 if not considered a safety risk for the patient).

Criteria for dose interruption within cycle:

- ANC $<$ 1,000/mcL.
- Platelet count $<$ 50,000/mcL.

Re-treatment within the cycle may only be started when ANC \geq 1,000/mcL and platelet count \geq 50,000/mcL.

Doses omitted for toxicity within a cycle are not replaced or restored within the same cycle (meaning that the cycle remains 28 days regardless of the number of doses of taken).

If these conditions are not met, anastrozole treatment may be continued but treatment with PD 0332991 must be delayed by one week. If, after a one-week delay, all toxicities have recovered within the limits described above, treatment with PD 0332991 can be resumed.

If the patient has not recovered after 2 weeks (including the scheduled 1-week off treatment period within a cycle) despite dose reduction to the lowest dose level, treatment with PD 0332991 will be permanently discontinued.

Adjuvant PD 0332991 may be interrupted for a maximum of 4 weeks due to intercurrent illness or surgery (discuss with study chair).

Anastrozole is administered in a continuous regimen and therefore no re-treatment criteria apply.

6.4 Re-Treatment Criteria for Cycle 5

Cycle 5 Day 1 with PD 0332991 may begin only if:

- ANC \geq 1,500/mcL
- Platelet count \geq 100,000/mcL
- Non-hematologic toxicities have returned to baseline or Grade \leq 1 severity (or, at the Investigator's discretion, Grade \leq 2 if not considered a safety risk for the patient).

If these conditions are not met, anastrozole treatment will be continued but treatment with PD 0332991 will be delayed by one to three weeks. If all toxicities have recovered within the limits described above within 3 weeks, treatment with PD 0332991 for Cycle 5 will be initiated. If the patient has not recovered after a 3 week delay, treatment with PD 0332991 will be permanently discontinued and patients should proceed to surgery within 3 to 5 weeks after the last dose of PD0332991 (Cycle 4 Day 21) if possible.

Anastrozole is administered in a continuous regimen and therefore no re-treatment criteria apply.

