10.3 Post Surgery Treatment Calendar

Patients who had a Ki67<10% on the neoadjuvant C1D15 tumor biopsy in the endocrine resistant cohort (before or after activation of Amendment #7) and the 26 patients who enrolled initially to the main trial (PIK3CA WT or mutant cohort) who required PD 0332991 to achieve complete cell cycle arrest have the option of restarting PD 0332991 in combination with anastrozole for adjuvant treatment (23 cycles after surgery). These patients will need to be consented and screened for the adjuvant portion of the study, and may only begin treatment with adjuvant PD 0332991 if they meet the eligibility criteria in Section 3.4 and if they have provided informed consent.

PD 0332991 should be re-started at least 4 weeks after the completion of chemotherapy and radiation therapy if these treatments were planned. Anastrozole may be started earlier while the patient receives radiation therapy if desired. After completion of PD 0332991, patients should continue standard of care hormonal therapy (for example anastrozole) to complete at least 5 years of therapy. Further therapy after that is at the discretion of treating physician.

	Screening	Adjuvant Cycles 1-2		Adjuvant Cycles 3 to 23	End of C23 or early termination	Follow up
Day of cycle	-30 to 0	D1 +/- 3 days	D14 +/- 3 days	D1 +/- 7 days (C3, 6, 9, 12, 15, 18, 21)	4 weeks	+/- 8 weeks
TREATMENT						
Endocrine Therapy ^A		Daily				
PD 0332991		Days 1-21 each cycle				
CLINICAL ASSESSMENT						
Informed consent	X					
Concomitant medication	X	X		X	X	
H&P, PS	X	X		X	X	
Adverse event assessment	X	X	X	X	X	X
ECG	X					
Disease monitoring ^B	X			Per standard of care		
CBC+ differential	X	X	X	X	X	X
Serum chemistry ^C	X	X		X	X	X
Serum/urine pregnancy test ^G	X	X		X	X	
Drug compliance assessment ^D		X		X	X	
Research blood ^E		X		X (C12 only)	X	X

- A. Premenopausal women requires goserelin
- B. Disease monitoring is per standard of care.
- C. Serum chemistry is albumin, alkaline phosphatase, total bilirubin, bicarbonate, BUN, calcium, chloride, creatinine, glucose, potassium, total protein, SGOT/AST, SGPT/ALT, sodium.
- D. Patients will keep a pill diary (Appendix D).
- E. Research blood includes the collection of plasma, serum and whole blood for cfDNA.
- F. For patients who did not receive adjuvant PD 0332991 the follow up is yearly for 5 years post surgery or until recurrence whichever comes first.
- G. In premenopausal women only.

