11.0 DATA SUBMISSION SCHEDULE

Case report forms with appropriate source documentation will be completed according to the schedule listed in this section. Electronic data management systems will be used in this trial in collaboration with the Center for Biomedical Informatics core at Washington University.

ClinPortal is a web-based clinical studies data management system that will be used for capture of clinical data from this trial. The case report forms developed for this trial will be transformed to electronic format. An electronic study calendar will drive the study's data collection workflow. An Oracle database securely stores PHI in compliance with HIPAA and IRB regulations.

Identical study databases will be created in ClinPortal for each participating center; each center has access only to data from its own participants. Washington University, as the data coordinating center, has access to data from all sites.

Training in entering data in ClinPortal is required before a participating center will be given access to its site's database. The Center for Biomedical Informatics at Washington University offers monthly web-based training for external users; the schedule may be found at the following URL: <http://cbmi.wustl.edu/?q=clinportal-training-details>. Users must RSVP at least 3 days prior to the training sessions.

In addition, a participating center must have IRB approval of this protocol prior to initiation of ClinPortal data entry training, which must be completed prior to site study activation.

Case Report Form	Submission Schedule
Original Consent Form	Prior to (pre-) registration
Pre-registration Form Registration Form Eligibility Form Pre-Study Form	Prior to starting treatment
Treatment Form Labs Form	Every cycle
Adjuvant Form	Every cycle of adjuvant therapy
Toxicity Form	Continuous
Treatment Summary Form	Completion of treatment
Disease-Related Assessment Form	Day 1 of each cycle and end of Cycle 4
MedWatch Form	See Section 7.0 for reporting requirements
Surgery Form	1 month post surgery
Correlative Studies Form	Refer to Section 9.0
Follow-Up Form	Annually for 5 years after surgery

Any queries generated by Washington University must be responded to within 28 days of receipt by the participating site. The Washington University research team will conduct a regular review of data status at all secondary sites, with appropriate corrective action to be requested as needed.

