Adverse Events: All eligible patients that have initiated treatment will be considered evaluable for assessing adverse event rate(s). The maximum grade for each type of adverse event will be recorded for each patient using the NCI-CTCAE v4.0, and frequency tables will be reviewed to determine patterns. Additionally, the relationship of the adverse event(s) to the study treatment will be taken into consideration.

Ki67 suppression on Cycle 1 Day 1, Cycle 1 Day 15 and surgery: Following the approach of Dowsett et al. [26], the percent change in the Ki67 level from baseline will be determined on the log scale. A 95% t-confidence interval for the mean percent change in the Ki67 level from baseline will be constructed (if appropriate). The rate of complete cell cycle arrest on C1D1, C1D15, and surgery will be described by contingency tables compared by McNemar tests. Using trajectory analysis, we will also assess the association between distinct patterns of Ki67 change over time and clinical outcomes. Specifically, trajectory groups will be formulated to describe clusters of individuals with similar temporal patterns of Ki67 over time using finite mixture models with SAS procedure TRAJ. This method enables identification of the number of discrete trajectory types, and characterization of the shape and estimation of the prevalence of each type. We will choose the best models based on statistical tests (including Bayesian and Akaike information criterion, each of which test goodness-of-fit) and clinical judgment.

To assess the long term outcomes of patients treated in this trial: The long-term outcomes (i.e., pathologic complete response (pCr), local and distant recurrence, etc, as defined in section 12.4) will also be assessed in the PIK3CA wild and mutnt cohorts (separately and combined) and the endocrine resistant cohort, respectively. The categorical outcome will be summarized using contingency tables and compared by Fisher's exact test, while the time-to-event outcomes will be described using Kaplan-Meier product limit estimators and compared by log-rank test.

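### Section 6.3 makes the start of every adjuvant PD 0332991 cycle conditional on blood counts, but calendar 10.3 schedules a Day 1 count in only 9 of 23 cycles

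*Combined protocol and SAP*

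**What the plan says.** The rule is in section 6.3, whose title names its scope: "6.3 Re-Treatment Criteria for Neoadjuvant Cycles 1-4 and Adjuvant Therapy". It opens with "A new cycle of treatment with PD 0332991 may begin only if" and then lists an ANC of at least 1,000/mcL, platelets of at least 50,000/mcL, and recovery of non-hematologic toxicity. No adjuvant cycle is exempt. If the conditions are not met, PD 0332991 is delayed by a week.

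The schedule is in section 10.3. PD 0332991 is given on Days 1 to 21 of each adjuvant cycle, for up to 23 cycles (also section 5.6). A CBC with differential is marked at screening, at D1 and D14 of Cycles 1 and 2, at the visits headed "D1 +/- 7 days (C3, 6, 9, 12, 15, 18, 21", at the end of treatment and in follow-up. No footnote to 10.3 adds a count.

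Section 11.0 bears on intent. It lists a Labs Form as due every cycle, without limiting this to the neoadjuvant phase, and an Adjuvant Form as due "Every cycle of adjuvant therapy".

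**The concern.** Only a blood count can show whether the ANC and platelet conditions are met. If no count is scheduled, a site working from the adjuvant calendar starts the cycle without the check that section 6.3 makes mandatory. A site working from 6.3 draws a count that the calendar does not list. In a multicenter trial, practice can then differ according to which section a site follows.

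Section 8.1.5 makes this practical. Patients receive enough drug to last until the next study visit. A woman seen at Cycle 3 would therefore go home with supply for Cycles 3, 4 and 5, and would start two of those cycles with no scheduled contact.

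The check matters for this drug. For the cited letrozole combination arm (n = 84), section 1.7 reports "neutropenia (grade 1/2: 23%; grade 3: 55%, grade 4: 6" percent. Section 1.4.5 names neutropenia and thrombocytopenia as the most common grade 4 events in the single-agent studies.

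**Working it through.** The plan states no total to reproduce, so the check is a direct count of calendar 10.3 against the rule in 6.3.

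**Inputs**
- Adjuvant cycles: up to 23 (sections 5.6 and 10.3).
- Cycles subject to the start rule: all of them (6.3).
- Day 1 CBC visits in Cycles 1 and 2: 2 (10.3).
- Day 1 CBC visits in Cycles 3 to 23: Cycles 3, 6, 9, 12, 15, 18 and 21, so 7 (10.3).
- Cycle length 28 days, with 21 dosing days (5.1 and 10.3).

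**Cycle starts with and without a scheduled count**
- With: 2 + 7 = 9; 9/23 = 39.1%.
- Without: 23 − 9 = 14; 14/23 = 60.9%.
- The 14 are Cycles 4, 5, 7, 8, 10, 11, 13, 14, 16, 17, 19, 20, 22 and 23.
- The D14 counts in Cycles 1 and 2 and the end-of-treatment count add no Day 1 count.

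**Spacing of scheduled counts from Cycle 3 to Cycle 21**
- Nominal gap: 3 × 28 = 84 days.
- With ±7 days at each visit: 84 − 14 = 70 days to 84 + 14 = 98 days.
- Planned PD 0332991 doses from one such visit to the next: 3 × 21 = 63.

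**Timing of the counts that are scheduled**
In Cycles 3 to 21 the window runs to 7 days after Day 1, and nothing in 10.3 says the count must precede the first dose. A visit inside its window can therefore still miss the 6.3 condition.

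**Comparison with the neoadjuvant phase**
Calendar 10.2 schedules a CBC at D1 of each repeat cycle under the same rule (Cycles 2 to 4), so 0 of 3 lack one. This comparison covers only the start-of-cycle part of 6.3. Calendar 10.2 has no mid-cycle count for the within-cycle interruption rule.

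**The case against.** **Silence is not contradiction.** Calendar 10.3 does not say that a count is unnecessary in the other cycles, and 6.3 stays binding. A site that starts Cycle 4 without a count breaches 6.3; 10.3 gives it no permission. This stands, so the finding is a misalignment between rule and calendar and not a waiver of the rule. It does not close the gap, because visits and drug supply follow the calendar.

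**The calendars are not complete lists.** Calendar 10.2 also lacks the mid-cycle counts that the interruption rule could use. That is true, but the two rules differ. The interruption rule acts on a result when there is one; the start rule is a precondition and cannot be met without a result.

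**Section 11.0 may already expect labs each cycle.** The Labs Form line is the best counter-evidence in the documents. It is a submission time, and the separate Adjuvant Form leaves its scope unclear. If it does show intent, it shows that 10.3 is incomplete.

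**The risk may be small and the spacing deliberate.** These women have already had PD 0332991 in this trial, and they have counts at screening, through Cycles 1 and 2, and at Cycle 3. Section 5.1, writing about Cycle 5 before surgery, says "recovery of neutropenia is usually prompt after stopping PD 0332991". This lowers the likely harm but does not satisfy 6.3 in the 14 cycles.

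A reader might infer more than the documents support:
- *That the data system would fail to prompt a count.* Section 11.0 says "An electronic study calendar will drive the study's data collection workflow", but not that this calendar is built from 10.3, and the same section asks for forms every cycle.
- *That the 55% and 6% neutropenia figures show how often the check would fail.* They come from first-line metastatic disease and are not rates at cycle start.
- *That maximum hematologic grade for secondary objective 9 would be understated.* Section 15.5 does say "The maximum grade for each type of adverse event will be recorded for each patient using the NCI-CTCAE v4.0". But a Day 1 count follows a week off drug and is poorly placed to catch the worst grade, and the Toxicity Form is continuous.

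**Conclusion.** The point holds as an inconsistency between a mandatory safety rule and the calendar meant to carry it out. Of 23 adjuvant cycle starts, 14 (61%) have no scheduled count. In Cycles 3 to 21, even the scheduled count may fall after dosing starts.

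This rests on two readings. The first is that 6.3 applies to every adjuvant cycle, as its title and wording say. The second is that the list of cycles in the 10.3 column heading is complete, as its explicit form indicates. Sites may draw extra counts as routine care, but the documents do not order them.

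How often the 6.3 limits would fail at the start of a later adjuvant cycle cannot be estimated from the documents. The matter concerns patient safety and uniform conduct in an optional phase. No test, power or sample size depends on it. It should be corrected, but it does not threaten the trial's inference.

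A reader might also infer that relaxing 6.3 to match the calendar would do equally well. Nothing in the documents says that adjuvant cycles were meant to be exempt, and that change would weaken a stated safety check.

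**What to change.** In calendar 10.3, mark a CBC for every adjuvant cycle. Add a footnote requiring a local CBC with differential before the first PD 0332991 dose of each adjuvant cycle, with the result checked against 6.3 before dosing and recorded on the per-cycle form already due under section 11.0. Tying the count to the first dose also removes the problem of a visit window that extends past Day 1. The clinic visits can stay at every third cycle.

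The cost is up to 14 more routine local draws per woman who completes 23 cycles. For the 26 main-trial patients named in section 3.5.1, the ceiling is 14 × 26 = 364 draws, if all enroll and complete. Draws for any endocrine resistant patients who take up adjuvant treatment come on top, and the documents do not fix their number. Since 6.3 already presupposes these counts, the amendment schedules a check that the protocol requires.

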11.0 DATA SUBMISSION SCHEDULE

Case report forms with appropriate source documentation will be completed according to the schedule listed in this section. Electronic data management systems will be used in this trial in collaboration with the Center for Biomedical Informatics core at Washington University.

ClinPortal is a web-based clinical studies data management system that will be used for capture of clinical data from this trial. The case report forms developed for this trial will be transformed to electronic format. An electronic study calendar will drive the study's data collection workflow. An Oracle database securely stores PHI in compliance with HIPAA and IRB regulations.

Identical study databases will be created in ClinPortal for each participating center; each center has access only to data from its own participants. Washington University, as the data coordinating center, has access to data from all sites.

Training in entering data in ClinPortal is required before a participating center will be given access to its site's database. The Center for Biomedical Informatics at Washington University offers monthly web-based training for external users; the schedule may be found at the following URL: <http://cbmi.wustl.edu/?q=clinportal-training-details>. Users must RSVP at least 3 days prior to the training sessions.

In addition, a participating center must have IRB approval of this protocol prior to initiation of ClinPortal data entry training, which must be completed prior to site study activation.

Case Report Form	Submission Schedule
Original Consent Form	Prior to (pre-) registration
Pre-registration Form Registration Form Eligibility Form Pre-Study Form	Prior to starting treatment
Treatment Form Labs Form	Every cycle
Adjuvant Form	Every cycle of adjuvant therapy
Toxicity Form	Continuous
Treatment Summary Form	Completion of treatment
Disease-Related Assessment Form	Day 1 of each cycle and end of Cycle 4
MedWatch Form	See Section 7.0 for reporting requirements
Surgery Form	1 month post surgery
Correlative Studies Form	Refer to Section 9.0
Follow-Up Form	Annually for 5 years after surgery

Any queries generated by Washington University must be responded to within 28 days of receipt by the participating site. The Washington University research team will conduct a regular review of data status at all secondary sites, with appropriate corrective action to be requested as needed.

12.0 MEASUREMENT OF EFFECT

12.1 Neoadjuvant Treatment

Complete cell cycle arrest: This is defined as $\text{Ki67} \leq 2.7\%$, which will be assessed at C1D1, C1D15, and surgery. In patients without C1D15 Ki67, Ki67 on D15 of subsequent cycles could be used instead.

Clinical Evaluation: Prior to Cycle 0 (or performed during pre-registration for study NCI 9170), and at the end of each neoadjuvant treatment cycle cycles (that is, at the end of Cycles 1-4) the longest axis and the perpendicular axis of the measurable lesion should be measured and recorded in metric notation by tape, ruler or caliper technique on the case report forms.

Radiologic evaluation of tumor size: Mammogram and ultrasound imaging will be performed prior to Cycle 0 (or performed during pre-registration for study NCI 9170) and at the end of Cycle 4 combination therapy for bidimensional measurement of the tumor.

WHO criteria will be used to assess clinical and radiologic responses.

Complete Response (CR) is defined as the disappearance of all known disease based on a comparison between the pre-treatment measurements and the measurements taken at the completion of neo-adjuvant therapy (that is, at the end of cycle 4 neo-adjuvant combination therapy). In addition there is no appearance of new lesions.

Partial Response (PR) is defined as a 50% or greater decrease in the product of the bi-dimensional measurements of the lesion (total tumor size) between the pre-treatment measurements and the measurements taken at the completion of neo-adjuvant therapy (that is, at the end of cycle 4 neo-adjuvant combination therapy). In addition there can be no appearance of new lesions or progression of any lesion.

No Change (NC): a 50% decrease in total tumor size cannot be established nor has a 25% increase in the size of the lesion been demonstrated.

Progressive Disease (PD): A 25% or greater increase in the total tumor size of the lesion from its pretreatment measurements or the appearance of new lesions.

